3.3 Secondary Study Endpoints

Secondary endpoints include:

- patient satisfaction with telehealth visits as measured by the PSCC (see appendix II). In the PSCC each item is scored on a 1-5 scale, corresponding to statements ranging from strongly agree to strongly disagree.
- patient assessment of physician communication during a post-treatment visit as measured by the CAT (see appendix II). In the CAT each item is scored on a 1-5 rating scale, with higher scores indicating higher satisfaction with physician communication.
- patient distrust in the healthcare system as measured by the health care system distrust scale (see appendix II). Items are scored strongly disagree to strongly agree.
- physician ability to evaluate a patient during a telehealth visit as measured by the physician questionnaire (see appendix II). Individual items are scored yes, no or N/A
- physician satisfaction with post-treatment telehealth visit as measured by the modified physician satisfaction scale (see appendix II). Individual items are scored strongly disagree to strongly agree.
- patient and clinic costs for a telehealth visit

4.0 SUBJECT SELECTION AND WITHDRAWAL

4.1 Inclusion Criteria

1. Patients who underwent, currently undergoing or planned to start radiation treatment with curative, adjuvant or palliative intent, who have not yet had their first post-treatment visit
2. Age ≥ 18
3. KPS score ≥ 60
4. Patients must be capable to read and speak English and provide study specific informed consent prior to study entry
5. Patients must have access to a computer or smartphone, email and internet connection at home or at a location convenient to them on which they would be willing to do a telehealth study
6. Pennsylvania or New Jersey residents*

*Telehealth visits for New Jersey residents will only be performed by physicians with a current medical license issued by the state of New Jersey.

4.2 Exclusion Criteria

1. Patients under the age of 18

2. KPS <60%
3. No access to a computer, smartphone or internet
4. Unable to read and/or speak English
5. Decisionally impaired patients
6. Patients not residing in Pennsylvania or New Jersey

4.3 Gender/Minority/Pediatric Inclusion for Research

This protocol will enroll women and men with any malignancy or benign condition treated with radiation therapy and will include minorities in the research protocol. Pediatric patients will be excluded.

4.4 Subject Recruitment and Screening

Patients who are 18 years of age or older with a cancer or benign diagnosis are eligible for the study. Patient can be recruited from the Principal investigator, co-investigator or referring physicians' clinical practices. Potential study subject should be referred to Principal investigator, co-investigator or study designated research nurse/associate. Principal investigator, co-investigator, or designated research nurse/associate will screen and determine the final eligibility of the subject for enrollment.

4.5 Early Withdrawal of Subjects

4.5.1 When and How to Withdraw Subjects

Patients will be informed that they have the right to withdraw from the study at any time for any reason, without prejudice to their medical care. The investigator also has the right to withdraw patients from the study for any of the following reasons:

1. Intercurrent illness
2. Patient request
3. Non-compliance
4. Administrative reasons
5. Patients may withdraw from the study voluntarily at any time;

At the time of withdrawal, all study procedures outlined for the End of Study visit should be completed. The primary reason for a patient's withdrawal from the study is to be recorded in the source documents.

4.5.2 Data Collection and Follow-up for Withdrawn Subjects

According to FDA regulations, when a subject withdraws from the study, the data collected on the subject to the point of withdrawal remains part of the study database and may not be removed.

A subject who is withdrawing needs to state whether he/she wishes to provide continued follow-up and further data collection subsequent to withdrawal from the interventional portion of the study.

If a subject withdraws from the interventional portion of the study, but agrees to continued follow-up of associated clinical outcome information as described in the previous bullet, the subject will continue follow up visit and evaluation per the protocol.

If a subject withdraws from the interventional portion of a study and does not consent to continued follow-up of associated clinical outcome information, study data related to the subject collected prior to the subject's withdrawal from the study will included in the study analysis. However, the subject's clinical data will not be used for dose escalation determination.

5.0 STUDY DRUG/THERAPY

5.1 Description

Through the new Telehealth service provided by TJUH, patients are able to connect with TJUH doctors through a smartphone, tablet or computer to receive real-time care, such as on demand visits, scheduled online visits and remote second opinions, from any location convenient to them.

In this trial, patients will receive their first post radiation treatment follow up as a virtual visit using Telehealth.

5.2 Treatment Regimen

Following obtaining informed consent, patients will return for their first post-treatment visit as a virtual visit via Telehealth. During the visit the patients will use the application from their own home or any other off-campus location that is convenient for them. Patients will meet with a study representative to be introduced to the application.

Following the visit, patients will be emailed to ask to complete a survey regarding their perceptions of the visit.

5.3 Risks

Risks of the study include potential anxiety caused to the patients

5.4 Method for Assigning Subjects to Treatment Groups

This is a single arm study

5.5 Preparation and Administration of Study Therapy

Patients will be shown how to download the application to their electronic device and they will be instructed on the use of the application. A demonstration of the software will be done in the office to ensure patient understanding. A written hand out regarding application use will also be provided to the patients. Patients will receive follow up instructions including date and time of post-treatment visit.

5.6 Subject Compliance Monitoring

Compliance in the study is defined as subject return for post-treatment visit. Patients who fail to return for post-treatment visit will be deemed non-compliant.

6.0 STUDY PROCEDURES

6.1 Study Visit Schedule

Screening:

Potential candidates for the study will be identified by their treating radiation oncologist. Eligibility of patients will be verified based on eligibility criteria (section 4.1). Those eligible patients will receive detailed information about the study. Patients will be informed of possible risk and benefits. Informed consent will be obtained from patients. Demographics and patient KPS will be assessed at the time of the screening visit

Visit 1:

Patients will undergo their first post-treatment visit as a virtual telehealth visit. Following the visit the treating physician will fill out the physician questionnaires on paper or online, while patients will be emailed a patient-specific link to a survey. Physicians will have 2 weeks following the date of the visit to complete the survey. Patients will have up to 4 weeks after the visit to complete the survey. Patients will receive weekly reminder emails regarding the survey up to 3 times after the visit. Patients will also have the option to fill out a paper survey (provided at the time of treatment discharge with the discharge instructions) and mail it into the office.

Follow-up

There will be no subsequent follow up

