Schema	
Subject Signs Consent
 
↓
 
Eligibility is checked; demographics obtained
 
↓
 
Subject registered to Jeff Trial Data base
 
↓
 
At completion of radiation treatment, subject is provided with a date and time for post-treatment follow up
 
↓
 
Subject has post-treatment follow up as a telehealth visit
 
↓
 
Both treating physician and patient are emailed links to respective surveys immediately following visit
 
↓
 
Subject is emailed an online reminder week after completion of follow-up visit and has until 4 weeks from the date of the visit to complete

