6.1.1 Study Flowchart

	Screening visit	Post-treatment visit	Sent to patient following visit
Informed consent	X		
Background information	X		
KPS	X		
Patient Satisfaction with Cancer Care Scale ^b			X
Communication assessment tool ^b			X
Health care system distrust tool ^b			X
Physician questionnaire ^a		X	
Modified physician satisfaction scale ^a		X	

- a. Physicians are to complete surveys and satisfaction scale within 2 weeks following the visit.
- b. Patients are to complete surveys within 4 weeks following the visit. They will be emailed reminders weekly following the visit.

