Showed care and concern					
Spent the right amount of time with me					

Health care system distrust scale

The next questions are about your opinion of the health care system in general. When we refer to the health care system, we mean hospitals, health insurance companies, and medical research. For each statement below, please indicate how strongly you agree or disagree

	Strongly agree (5)	Agree (4)	Not sure (3)	Disagree (2)	Strongly disagree (1)
Medical experiments can be done to me without my knowing about it					
My medical records are kept private					
People die every day because of mistakes by the health care system					
When they take my blood, they do tests they don't tell me about					
If a mistake were made in my health care, the health care system would try to hide it from me					
People can get access to my medical records without my approval					
The health care system cares more about holding costs down than it does about doing what is needed for my health					
I receive high-quality medical care from the health care system					
The health care system puts my medical needs above all other considerations when treating my medical problems					
Some medicines have things in them that they don't tell you about					

Physician questionnaire

	Yes	No	Not applicable
Were you able to assess the patient's symptoms?			
Were you comfortable assessing treatment related toxicity?			
Was a medication assessment done?			
Was KPS assessed and documented?			
If this was a telehealth visit, did you feel the need to bring the patient in to the office for further evaluation?			
Was patient provided with follow up instructions at the end of the visit?			
Was patient asked about follow up with other providers?			
Was patient provided with follow up labs and/or imaging instructions? Yes			
How long did today's visit take?	Today's visit took approximately _____ minutes		

Modified physician satisfaction scale

	Strongly agree (5)	Agree (4)	Not sure (3)	Disagree (2)	Strongly disagree (1)
I was able adequately to review this patient's laboratory results					
I was able adequately to review this patient's imaging					
I was able to elicit an adequate history from this patient					
I was able to communicate facts adequately to this patient					
I think this patient was satisfied with this clinical encounter					
My ability to evaluate this patient was significantly hampered because s/he was seen via televideo rather than in person					

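### Physician forms worded for the day of the visit may be completed up to 2 weeks later, possibly after an in-person visit, and carry no completion date

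*Combined protocol and SAP*

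**What the plan says.** Timing is addressed in three places.

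- **Study Summary, Schema:** "Both treating physician and patient are emailed links to respective surveys immediately following visit".
- **Section 6.1:** the physician may use paper or an online form, and "Physicians will have 2 weeks following the date of the visit to complete the survey".
- **Section 6.1.1, flowchart:** both physician forms sit in the post-treatment visit column, but footnote a reads "Physicians are to complete surveys and satisfaction scale within 2 weeks following the visit".

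The physician questionnaire in Appendix II includes "Were you able to assess the patient's symptoms", "Were you comfortable assessing treatment related toxicity" and "did you feel the need to bring the patient in to the office for further evaluation", each answered yes, no or not applicable. It ends with "How long did today's visit take", answered as an approximate number of minutes.

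Section 1.5 lets a physician who cannot assess the patient adequately by telehealth, or who is worried about something, ask the patient to come in. Section 3.3 makes the questionnaire the measure of how well the physician could evaluate the patient by telehealth. It also lists patient and clinic costs as an endpoint. Section 7.3 says that every enrolled subject is analysed.

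**The concern.** The form and its completion window do not fit together. A question about today's visit assumes that the answer is given that day, but the rule accepts an answer on day 14. Two kinds of error can follow on late forms.

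1. **Memory.** Minutes are recalled after other patients have been seen. This is the only duration asked for on any form shown, in a study whose third aim concerns time and money.
2. **Hindsight.** If the patient has been called in and examined before the form is completed, the physician knows what the telehealth visit missed or confirmed. The endpoint should reflect the telehealth encounter alone. The patients exposed are those for whom that encounter was inadequate or worrying, and they are the most informative for this endpoint.

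If late forms cannot be told apart from prompt ones, neither error can be examined at analysis.

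**Working it through.** No sample size, power or alpha in the plan depends on the 2-week window, so there is no stated figure to reproduce. The check sets the sections side by side.

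**Step 1: is the window really 2 weeks for both forms?** Yes. Section 6.1 and footnote a agree, and footnote a names the satisfaction scale as well. The Schema fixes when the link is sent, not when the form is completed.

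**Step 2: does any section put the form before an in-person visit?** No. Section 1.5 permits the in-person visit and sets no order relative to the form. Sections 5.2, 6.1 and 7.2 set none either.

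**Step 3: which items are exposed to hindsight?** The questionnaire has 8 yes/no items.
- Two (symptoms and toxicity) are judgements about the telehealth assessment and are exposed.
- One (the need to bring the patient in) is largely settled once the patient has been called in.
- The other five record whether something was done: medication assessment, KPS, follow-up instructions, other providers, and laboratory or imaging instructions. They are little exposed to hindsight.

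The modified physician satisfaction scale has further ability items: review of laboratory results, review of imaging, history taking, whether evaluation was hampered, and whether the physician was less sure of having all the information. These carry the same exposure under the same window.

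**Step 4: can late forms be found afterwards?** Not reliably. The screening form has a date line, but the physician forms as shown have none. Section 8.3 asks for dates on corrections, not on completion. Online forms might be time-stamped, but the documents do not say so, and paper is allowed.

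**Step 5: is duration captured another way?** No section says that it is logged at the visit or taken from the telehealth platform.

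**Step 6: can the effect be sized?** The share of forms open to hindsight is

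share = P(patient called in) × P(seen in person before the form is completed, given called in).

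The documents give neither factor. They also give no distribution of completion delay and no recall-error figure. The direction is open too: an in-person visit may show that telehealth missed something or that it was adequate.

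**Step 7: what is untouched?** The primary endpoint (section 3.2) is the accrual rate, which uses no physician form. The patient satisfaction test in sections 7.1 and 7.2 uses the PSCC, which patients complete.

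**The case against.** Two weeks is an outer limit, not a target. The link goes out at once and the flowchart places the forms at the visit, so many forms may be prompt. A grace period for busy clinicians in an unfunded pilot is a fair trade against missing forms. Section 7.2 plans no test on these items. All of this stands. It keeps the point minor and is why the outer limit should remain.

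Several stronger readings are tempting, but the documents do not support them.

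- **That visit duration is generally recalled.** This holds only for forms completed late.
- **That the error can be sized by rounding.** Rounding an assumed 15-minute visit to the nearest 5 minutes gives at most 2.5/15 = 17% per visit. But the form asks for an approximate figure, so the same rounding would occur on the day and says nothing about delay. It also largely averages out. If it is uniform within ±2.5 minutes, its SD is 5/√12 = 1.44 minutes, and over the 60 patients expected in section 7.1 the standard error is 1.44/√60 = 0.19 minutes, or 1.2% of 15.
- **That 10–20% of assessment answers are affected.** No call-in rate is given. Even if 10–20% were assumed (6 to 12 of 60), it would be a ceiling, reached only if every such patient was seen before the form was completed.
- **That the yes/no items are the only effectiveness measure, or that the minutes are the stated input to clinic savings.** The satisfaction scale also has ability items, and no section links the minutes to the cost calculation.
- **That late forms cannot be identified at all.** Online submissions may carry a time stamp; the documents are silent.

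**Conclusion.** The point holds as a minor design improvement. The plan allows 14 days for a form written for day 0, does not require it before an in-person visit, and shows no field that would reveal which forms were late. For late forms, the minutes depend on memory and the symptom, toxicity and ability items may reflect later findings. This affects the secondary endpoint on the physician's ability to evaluate the patient. If the minutes are used for time or cost, it affects those results too.

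The size and direction of any bias cannot be computed from the documents. The conclusion assumes only that some forms are completed after the visit day and that some patients called in are seen before their form is completed. The rules permit both; neither is certain.

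**What to change.** - **Section 6.1 and footnote a:** ask for the physician questionnaire and the ability items of the satisfaction scale on the day of the visit and before any in-person visit. Keep 2 weeks as the outer limit so that late forms are still accepted. This governs when the form is completed; it does not alter who is called in or when.
- **Physician forms in Appendix II:** record the start and end time of the visit at the visit. Add a completion date and a yes/no field for whether an in-person visit has already taken place.
- **Section 7.2:** keep all forms in the main summary, consistent with section 7.3. Report the ability items with and without forms completed after the visit day or after an in-person visit.

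Forms completed after an in-person visit should not be dropped from the main summary. They belong to the patients most likely to have a No on the ability items, so excluding them would tend to raise the apparent ability to assess by telehealth.

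The cost is a short edit to section 6.1 and its footnote, one sentence in section 7.2, a few extra form fields and some flagged forms.

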1.5 Dose Rationale and Risk/Benefits

If during the telehealth visit the treating physician feels he or she is unable to fully assess the patient, or has any concerns, he or she will ask the patient to come in for an in person visit.

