3.0 STUDY DESIGN

3.1 General Design

This is a single arm pilot feasibility study examining a telehealth visit for the first post radiation treatment visit. Patients will be asked to fill out a questionnaire within a week of the visit. There will be no subsequent follow up per trial. The expected enrollment duration of the study is 24 months. The overall study duration is expected to be 32 months.

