In addition to meeting inclusion criteria, patients are ineligible for enrollment if any of the following exclusion criteria are met.

- Patients under the age of 18
- KPS <60%
- No access to a computer, smartphone or internet
- Unable to read and/or speak English
- Decisionally impaired patients
- Patients not residing in Pennsylvania or New Jersey

Checklist for Screening Visit:

Informed Consent for Trial Obtained	
All Sections of CRF Completed	
Inclusion/Exclusion Criteria Evaluated	
Based on screening patient appears eligible	

TELEPORT Study Case Report Form (CRF)—Follow up Visit
Patient Satisfaction with Cancer Care Scale (PSCC)

Below is a list of statements regarding your recent post-treatment visit. Please indicate your response

	Strongly agree (1)	Agree (2)	Neutral (3)	Disagree (4)	Strongly disagree (5)
I felt my concerns were understood					
I felt I was treated with courtesy and respect					
I felt included in decisions about my health					
I was told how to take care of myself					
I felt encourages to talk about my personal health concerns					
I felt I had enough time with my doctor					
My questions were answered to my satisfaction					
Making an appointment was easy					
I knew what the next step in my care would be					
I feel confident in how I deal with the health care system					
I was able to get the advice I needed about my health issues					
I knew who to contact when I had a question					
I received all the services I needed					
I am satisfied with the care I received					
The doctors seemed to communicate well about my care					
I received high quality care from my regular doctor					
I received high quality care from my specialists					
My regular doctor was informed about the results of the tests I got					

Communication assessment tool (CAT)

Please use this scale to rate the way the doctor communicated with you.

	Poor (1)	Fair (2)	Good (3)	Very good (4)	Excellent (5)
Greeted me in a way that made me feel comfortable					
Treated me with respect					
Showed interest in my ideas about my health					
Understood my main health concerns					
Paid attention to me(looked at me, listened carefully)					
Let me talk without interruptions					
Gave me as much information as I wanted					
Talked in terms I could understand					
Checked to be sure I understood everything					
Encouraged me to ask questions					
Involved me in decisions as much as I wanted					
Discussed next steps, including any follow up plans					

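### A patient called back to the office may complete the PSCC and CAT after that visit and rate it instead of the telehealth visit, and the plan has no field or rule to separate the two

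*Combined protocol and SAP*

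**What the plan says.** **Survey window.** Section 6.1 states "Patients will have up to 4 weeks after the visit to complete the survey". The Schema in the Study Summary agrees (the subject "has until 4 weeks from the date of the visit to complete"), as does the footnote to the flowchart in 6.1.1: "Patients are to complete surveys within 4 weeks following the visit". Section 3.1 differs: "Patients will be asked to fill out a questionnaire within a week of the visit".

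**Delivery.** The Schema has the survey link sent at once: "Both treating physician and patient are emailed links to respective surveys immediately following visit". Section 6.1 makes that link specific to the patient and allows up to three weekly reminders. It also offers a paper form, "provided at the time of treatment discharge with the discharge instructions". The Study Summary places the follow-up visit 3 to 8 weeks after radiation ends, so the paper form is in the patient's hands weeks before the visit.

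**Call-back.** Under section 1.5, if the physician cannot fully assess the patient or has any concern, "he or she will ask the patient to come in for an in person visit". No expected rate or timing is given.

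**Wording of the scales (Appendix II).** The PSCC opens with "Below is a list of statements regarding your recent post-treatment visit". The CAT instruction asks how the doctor communicated and identifies no visit.

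**What is recorded.** The patient survey pages, as shown, have no visit date, no completion date and no question about an office visit. The physician questionnaire has one yes/no/not-applicable item on whether the physician felt a need to have the patient come in. It does not ask whether or when the patient came.

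**Attribution and analysis.** Section 3.3 assigns the PSCC score to telehealth visits, and section 2.2 does the same for communication. Section 7.2 tests the mean PSCC score and estimates the mean CAT rating. Sections 7.2 and 7.3 have no rule for surveys completed after an office visit.

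**The concern.** Two secondary objectives concern the telehealth visit itself: satisfaction with it, and the physician's communication during it. For a patient who was called back, attended, and only then opened the survey, the most recent visit is the office visit. The PSCC wording can be read as pointing to that visit, and the CAT wording does not exclude it. Some PSCC items, such as those on time with the doctor and services received, could plausibly be answered differently after an office visit.

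These patients are not a random subset. They are the ones whose telehealth visit left the physician unable to assess them fully or with a concern. If their answers describe a different visit, the scores lose information where telehealth was least sufficient in the physician's view. The satisfaction score also carries a formal test in 7.2. The undated paper form adds a smaller problem: its timing relative to either visit cannot be read from the form.

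**Working it through.** **1. The plan's own figure.** Section 7.1 gives n = 60, a true PSCC mean of about 90%, SD about 5%, a comparison value of 80%, alpha 0.05, and power above 90%. Power from the noncentral t distribution exceeds 99.99%, one- or two-sided, against 80 or against the 75 used in 7.2. The stated bound is reproduced with a wide margin: against 80, 4 patients (one-sided) or 5 (two-sided) already give 90%.

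**2. Standard error.** SE = SD/√n = 5/√60 = 0.645 points. This takes all 60 patients as returning the survey.

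**3. Shift in the mean.** Shift = f × g × d, where
- f = share of patients called back,
- g = share of those who answer after attending the office visit,
- d = change in their score, in points on the percentage scale of 7.1.

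The documents give none of the three, so every value below is an assumption.

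| f | g | d | Shift (points) | Shift / SE |
|---|---|---|---|---|
| 10% (6 patients) | 100% | 5 | 0.10 × 1 × 5 = 0.5 | 0.8 |
| 20% (12 patients) | 100% | 10 | 0.20 × 1 × 10 = 2.0 | 3.1 |
| 10% | 50% | 5 | 0.10 × 0.5 × 5 = 0.25 | 0.4 |
| 20% | 50% | 10 | 0.20 × 0.5 × 10 = 1.0 | 1.5 |

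A wider range (f 5% to 30%, g 50% to 100%, d 5 to 20) runs from 0.05 × 0.5 × 5 = 0.125 to 0.30 × 1 × 20 = 6 points. The sign of d is unknown, so each shift could go up or down.

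**4. Effect on the planned conclusion.** At a true mean of 90, the distance to the null is (90 − 80)/0.645 = 15.5 SE, or (90 − 75)/0.645 = 23.2 SE. Even a downward shift of 2 points leaves (88 − 80)/0.645 = 12.4 SE. The test result does not change.

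**5. Effect if the true mean lies at the null.** With a true telehealth mean of 80, a null of 80, n = 60 and SD held at 5, an upward shift raises the rejection rate as follows.

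| Upward shift | One-sided | Two-sided |
|---|---|---|
| 0 | 5% | 5% |
| 0.5 | 19% | 12% |
| 1 | 45% | 33% |
| 2 | 92% | 86% |

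**6. CAT.** The plan gives no SD, null value or test for the CAT, so no size can be put on it.

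**The case against.** The case on the other side is substantial.

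- **The pathway is narrow.** A patient must be called back, attend, and only then answer. No rate is documented for any step. The link is sent at once, reminders are weekly, and 3.1 asks for completion in one week. A reader might infer that the telehealth scores necessarily carry over the office visit. The documents support only that some may.
- **The direction is open.** A reader might expect an upward bias. A patient who had to make a second trip could equally score lower. Nothing in the documents settles this.
- **It is not uncheckable.** The physician item identifies patients the physician felt a need to see, so both scores can be re-run without them on data already planned. An emailed, patient-specific link also makes completion before the visit unlikely online. This stands, with limits. The item does not show whether or when an office visit took place. Dropping every flagged patient also discards those who answered before attending, and leaves only patients whose telehealth visit raised no such need. The documents do not say whether the online system stores completion times.
- **The wording is the protocol's own.** The protocol uses post-treatment visit as its name for the telehealth visit. That is clear for most patients. It is ambiguous for a called-back patient who answers late, and it does not help the CAT, which names no visit.
- **Call-back is part of the pathway.** A rating of telehealth plus any call-back could be a sensible target. The plan does not state that target; it attributes the scores to the telehealth visit.

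**Conclusion.** The attribution gap is real but modest. The long survey window, the call-back provision, scales that do not name the telehealth visit, and the absence of any rule in 7.2 and 7.3 together leave it unclear which visit a called-back, late-answering patient has rated.

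The size cannot be established from the documents. Under assumed call-back shares of 10% to 20%, all answering after the office visit, and assumed shifts of 5 to 10 points, the mean PSCC score moves by 0.5 to 2 points, or 0.8 to 3.1 standard errors. If only half answer late, those figures halve. The planned conclusion of 90 against 80 or 75 would stand. The estimate would still be biased, and the test would be affected if the true mean were close to the null.

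The accrual endpoint is untouched. So is the distrust scale as worded, since it asks about the health care system in general. The one-week and four-week texts contradict each other whatever the size of the bias, and must be reconciled.

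**What to change.** 1. **Name the visit.** Head the PSCC and the CAT: *Please answer about your telehealth (video) visit on [date].* Mark the paper form: *Complete only after your telehealth visit.*
2. **Record timing.** Add to the patient survey the completion date and one item: *Office visit since then: no / yes, date.*
3. **Reconcile the window.** Bring the one-week text in 3.1 into line with the four-week window in the Schema, 6.1 and the flowchart footnote.
4. **Add one analysis to 7.2.** Report PSCC and CAT for all responders, plus a sensitivity analysis that leaves out surveys completed after an office visit. Where dates are missing, use the physician item as the flag. Present it as a check on how far the result depends on these surveys, because the patients left out are a selected group.

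The cost is a few seconds per survey, one reconciled sentence and one extra table. The call-back provision stays as it is. One limit remains: PSCC items about care in general, such as those on the regular doctor and on specialists, will not become visit-specific through a new header.
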